4. STUDY OBJECTIVES

4.1 Primary Objective

- To assess the PK of lasmiditan in patients with episodic migraine during an acute migraine attack and during their inter-ictal period.

4.2 Secondary Objectives

- To assess the tolerability of a single dose of lasmiditan in patients with episodic migraine.
- To evaluate and compare the PK characteristics of major lasmiditan metabolites (M3, M7, M8, S,R-M18, and S,S-M18) in patients during an acute migraine attack and during the inter-ictal period.

4.3 Exploratory Objective

- To assess the effect of lasmiditan on exploratory biomarkers.

5. STUDY DESIGN

Study H8H-MC-LAHC is a multi-center, open-label study with 2 study periods to be conducted in patients with episodic migraine. Patients will receive 1 oral dose of lasmiditan during an acute migraine attack (Period 1), and 1 oral dose of lasmiditan during their inter-ictal period (Period 2). There will be a washout period of at least 1 week between doses.

All patients will participate in a screening visit. Eligible patients will be instructed to telephone the study site when they feel the onset of migraine symptoms, to arrange to attend for an immediate inpatient stay. Each patient must be admitted to the study site with continuing migraine symptoms within 28 days of the screening visit. Provided they are still experiencing migraine symptoms, patients will receive a single dose of 200 mg lasmiditan on arrival at the study site; this will be defined as Period 1, Day 1. The first dose of lasmiditan must be administered within 24 hours of onset of migraine symptoms; the time of administration will be defined as time = 0. Patients may be discharged from the study site after the last scheduled Day 2 assessment has been performed (24 hours postdose), at the discretion of the investigator, with subsequent Period 1 assessments performed on an outpatient basis. Patients will then telephone the study site again at the onset of their next migraine attack to arrange for a second inpatient stay, which should be scheduled for as soon as possible after the expected resolution of the migraine attack (ie, the next day or, if the migraine is expected to continue into the next day, the following day). This second visit should occur at least 1 week, and up to 4 weeks (but may be extended beyond 4 weeks if necessary, at the investigator's discretion) after their first lasmiditan dose, and will be defined as Period 2, Day 1. Provided the patient is still in their inter-ictal period (defined as not currently experiencing migraine symptoms) on arrival at the site, they will be readmitted as an inpatient and receive a single dose of 200 mg lasmiditan. Patients may be discharged from the study site after the last scheduled Day 2 assessment is complete, at the discretion of the investigator with subsequent Period 2 assessments performed on an outpatient basis. All patients will return for a follow-up visit 4 to 7 days after their last dose of lasmiditan.

Blood samples will be collected predose and up to 72 hours postdose in each period for the measurement of plasma concentrations of lasmiditan and its 5 major metabolites. Safety assessments performed during the study will include AEs, clinical laboratory evaluations, vital signs measurements, ECGs, and physical examinations.

Study governance considerations are described in detail in Appendix 3 of the protocol.

6. TREATMENT

The treatment administered will be a single oral dose of 200 mg lasmiditan on Day 1 of each treatment period.

Period	Treatment Name	Order in TFLs
Acute migraine attack	200 mg lasmiditan (Period 1)	1
Inter-ictal period	200 mg lasmiditan (Period 2)	2

7. SAMPLE SIZE JUSTIFICATION

Approximately 20 patients may be enrolled to ensure 12 patients with adequate PK data complete the study. Patients who do not complete both periods of the study may be replaced.

For area under the concentration versus time curve (AUC) or maximum observed drug concentration (C_{max}), assuming inter-patient CV% of 40% (based on previous studies) and a sample size of 12, the 90% confidence interval (CI) around the geometric mean of the within-patient ratios (migraine/inter-ictal) will have a half-width of 20.1% with 90% coverage probability.

8. DEFINITION OF ANALYSIS POPULATIONS

The “Safety” population will consist of all subjects who received at least one dose of study drug, and have at least one postdose safety assessment.

The “Pharmacokinetic” population will consist of all subjects who received at least one dose of study drug and have evaluable pharmacokinetic data. Subjects may be excluded from the PK summary statistics and statistical analysis if a subject has an adverse event of vomiting that occurs at or before 2 times median time of maximum observed drug concentration (t_{max}).

All protocol deviations that occur during the study will be considered for their severity/impact and will be taken into consideration when subjects are assigned to analysis populations.

9. STATISTICAL METHODOLOGY

9.1 General

Data listings will be provided for all data that is databased. Summary statistics and statistical analysis will only be presented for data where detailed in this SAP. For continuous data, summary statistics will include the arithmetic mean, arithmetic standard deviation (SD), median, min, max and N; for log-normal data (e.g. the PK parameters: AUCs and C_{max}) the geometric mean and geometric coefficient of variation (CV%) will also be presented. For categorical data, frequency count and percentages will be presented. Data listings will be provided for all subjects up to the point of withdrawal, with any subjects excluded from the relevant population highlighted. Summary statistics and statistical analyses will generally only be performed for subjects included in the relevant analysis population. For the calculation of summary statistics and statistical analysis, unrounded data will be used.

Mean change from baseline is the mean of all individual subjects’ change from baseline values. Each individual change from baseline will be calculated by subtracting the individual subject’s baseline value from the value at the timepoint. The individual subject’s change from baseline values will be used to calculate the mean change from baseline using a SAS procedure such as Proc Univariate.

Data analysis will be performed using SAS[®] Version 9.3 or greater.

9.2 Demographics and Subject Disposition

Subject disposition will be listed. The demographic variables age, sex, race, ethnicity, country of enrolment, site ID, body weight, height and body mass index will be summarized and listed. All baseline disease characteristics will also be summarized and listed.

9.3 Pharmacokinetic Assessment

9.3.1 Pharmacokinetic Analysis

Pharmacokinetic parameter estimates will be determined using non-compartmental procedures in validated software program (Phoenix WinNonlin Version 6.4 or later).

Plasma concentrations of lasmiditan (LY573144) and its 5 major metabolites (M3, M7, M8, S,R-M18, and S,S-M18) will be used to determine the following PK parameters, when possible:

Parameter	Units	Definition
C_{\max}	ng/mL	maximum observed drug concentration
t_{\max}	h	time of maximum observed drug concentration
$AUC(0-\infty)$	ng.h/mL	area under the concentration versus time curve from time zero to infinity
$AUC(0-t_{\text{last}})$	ng.h/mL	area under the concentration versus time curve from time zero to time t , where t is the last time point with a measurable concentration
% $AUC(t_{\text{last}}-\infty)$	%	percentage of $AUC(0-\infty)$ extrapolated
$t_{\frac{1}{2}}$	h	half-life associated with the terminal rate constant (λ_z) in non-compartmental analysis
CL/F	L/h	apparent total body clearance of drug calculated after extra-vascular administration (LY573144 only)
V_z/F	L	apparent volume of distribution during the terminal phase after extra-vascular administration (LY573144 only)
V_{ss}/F	L	apparent volume of distribution at steady state after extra-vascular administration (LY573144 only)
MR		metabolic ratio ^a

^a = no molar correction will be applied since the metabolites are very similar in molecular weight and within 5% of the molecular weight for lasmiditan.

Additional PK parameters may be calculated, as appropriate. The software and version used for the final analyses will be specified in the clinical study report. Any exceptions or special handling of data will be clearly documented within the final study report.

Formatting of tables, figures and abbreviations will follow the Eli Lilly Global PK/PD/TS Tool: NON-COMPARTMENTAL PHARMACOKINETIC STYLE GUIDE. The version of the tool effective at the time of PK analysis will be followed.

General PK Parameter Rules

- Actual sampling times will be used in the final analyses of individual PK parameters, except for non-bolus pre-dose sampling times which will be set to zero. For non-bolus, multiple dose profiles, the pre-dose time will be set to zero unless a time deviation falls outside of the protocol blood collection time window which is considered to impact PK parameter derivation.
- C_{\max} and t_{\max} will be reported from observed values. If C_{\max} occurs at more than one time point, t_{\max} will be assigned to the first occurrence of C_{\max} .
- AUC parameters will be calculated using a combination of the linear and logarithmic trapezoidal methods (linear-log trapezoidal rule). The linear trapezoidal method will be applied up to t_{\max} and then the logarithmic trapezoidal method will be used after t_{\max} . The minimum requirement for the calculation of AUC will be the inclusion of at least three consecutive plasma concentrations above the lower limit of quantification (LLOQ), with at least one of these concentrations following C_{\max} . AUC(0- ∞) values where the percentage of the total area extrapolated is more than 20% will be flagged. Any AUC(0- ∞) value excluded from summary statistics will be noted in the footnote of the summary table.
- Half-life ($t_{1/2}$) will be calculated, when appropriate, based on the apparent terminal log-linear portion of the concentration-time curve. The start of the terminal elimination phase for each subject will be defined by visual inspection and generally will be the first point at which there is no systematic deviation from the log-linear decline in plasma concentrations. Half-life will only be calculated when a reliable estimate for this parameter can be obtained comprising of at least 3 data points. If $t_{1/2}$ is estimated over a time window of less than 2 half-lives, the values will be flagged in the data listings. Any $t_{1/2}$ value excluded from summary statistics will be documented in the footnote of the summary table.
- A uniform weighting scheme will be used in the regression analysis of the terminal log-linear portion of the concentration-time curve.
- The parameters based on observed concentration at last quantifiable timepoint (C_{last}) will be reported.

Individual PK Parameter Rules

- Only quantifiable concentrations will be used to calculate PK parameters with the exception of special handling of certain concentrations reported below the lower limit of quantitation (BQL). Plasma concentrations reported as BQL will be set to a value of zero when all of the following conditions are met:
 - The compound is non-endogenous.
 - The samples are from the initial dose period for a subject or from a subsequent dose period following a suitable wash-out period.
 - The time points occur before the first quantifiable concentration.
- All other BQL concentrations that do not meet the above criteria will be set to missing.

- Also, where two or more consecutive concentrations are BQL towards the end of a profile, the profile will be deemed to have terminated and therefore any further quantifiable concentrations will be set to missing for the calculation of the PK parameters unless it is considered to be a true characteristic of the profile of the drug.

Individual Concentration vs. Time Profiles

- Individual concentrations will be plotted utilizing actual sampling times.
- The terminal point selections will be indicated on a semi-logarithmic plot.

Average Concentration vs. Time Profiles

- The average concentration profiles will be graphed using scheduled (nominal) sampling times.
- The average concentration profiles will be graphed using arithmetic average concentrations.
- The pre-dose average concentration for single-dose data from non-endogenous compounds will be set to zero. Otherwise, only quantifiable concentrations will be used to calculate average concentrations.
- Concentrations at a sampling time exceeding the sampling time window specified in the protocol, or $\pm 10\%$, will be excluded from the average concentration profiles.
- Concentrations excluded from the mean calculation will be documented in the final study report.
- A concentration average will be plotted for a given sampling time only if 2/3 of the individual data at the time point have quantifiable measurements that are within the sampling time window specified in the protocol or $\pm 10\%$. An average concentration estimated with less than 2/3 but more than 3 data points may be displayed on the mean concentration plot if determined to be appropriate and will be documented within the final study report.

Treatment of Outliers during Pharmacokinetic Analysis

Application of this procedure to all pharmacokinetic analyses is not a requirement. Rather, this procedure provides justification for exclusion of data when scientifically appropriate. This procedure describes the methodology for identifying an individual value as an outlier for potential exclusion, but does not require that the value be excluded from analysis. The following methodology will not be used to exclude complete profiles from analysis.

Data within an Individual Profile

A value within an individual profile may be excluded from analysis if any of the following criteria are met:

- For pharmacokinetic profiles during multiple dosing, the concentration of the pre-dose sample exceeds all measured concentrations for that individual in the subsequent post-dose samples.
- For pharmacokinetic profiles during single dosing of non-endogenous compounds, the concentration in a pre-dose sample is quantifiable.
- For any questionable datum that does not satisfy the above criteria, the profile will be evaluated and results reported with and without the suspected datum.

Data between Individual Profiles

1. If $n < 6$, then the dataset is too small to conduct a reliable range test. Data will be analyzed with and without the atypical value, and both sets of results will be reported.
2. If $n \geq 6$, then an objective outlier test will be used to compare the atypical value to other values included in that calculation:
 - a. Transform all values in the calculation to the logarithmic domain.
 - b. Find the most extreme value from the arithmetic mean of the log transformed values and exclude that value from the dataset.
 - c. Calculate the lower and upper bounds of the range defined by the arithmetic mean $\pm 3*SD$ of the remaining log-transformed values.
 - d. If the extreme value is within the range of arithmetic mean $\pm 3*SD$, then it is not an outlier and will be retained in the dataset.
 - e. If the extreme value is outside the range of arithmetic mean $\pm 3*SD$, then it is an outlier and will be excluded from analysis.

If the remaining dataset contains another atypical datum suspected to be an outlier and $n \geq 6$ following the exclusion, then repeat step 2 above. This evaluation may be repeated as many times as necessary, excluding only one suspected outlier in each iteration, until all data remaining in the dataset fall within the range of arithmetic mean $\pm 3*SD$ of the log-transformed values.

Reporting of Excluded Values

Individual values excluded as outliers will be documented in the final report. Approval of the final report will connote approval of the exclusion.

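### SAP 9.3.1 leaves outlier exclusion to discretion and, for six or more values, does not require the result with the value kept

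*SAP*

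**What the plan says.** The outlier part of SAP 9.3.1 begins with a general paragraph. It says that the procedure need not be applied to every analysis, that "this procedure provides justification for exclusion of data when scientifically appropriate", and that it identifies a value as a candidate for exclusion "but does not require that the value be excluded from analysis". It adds a limit: "The following methodology will not be used to exclude complete profiles from analysis".

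Specific rules follow:

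- Within one profile, for a questionable datum not met by the listed criteria: "the profile will be evaluated and results reported with and without the suspected datum".
- Between profiles, n < 6: "Data will be analyzed with and without the atypical value, and both sets of results will be reported".
- Between profiles, n ≥ 6: "an objective outlier test will be used to compare the atypical value to other values included in that calculation". The values are logged, the most extreme is set aside, and the mean ± 3 SD of the rest is formed. If the extreme value lies outside that range, "then it is an outlier and will be excluded from analysis". The step may be repeated while n ≥ 6.
- Reporting: "Individual values excluded as outliers will be documented in the final report". Approving the report counts as approving the exclusion.

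SAP 7 plans for 12 patients with adequate PK data from about 20 enrolled, so the main comparisons fall under the n ≥ 6 rule. SAP 9.3.2 adds no required sensitivity analysis for excluded values. SAP 9.1 lists all databased data.

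**The concern.** Two things are loose. Step 2(e) is worded as an instruction, while the paragraph above it makes exclusion a choice. What starts the test, a value that looks *atypical*, is not defined. The same data can therefore give more than one primary ratio within the plan, and the choice is settled after the ratios are known.

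The safeguard is also missing where it matters most. The SAP asks for both sets of results within a profile and in very small data sets, but not for the comparison that answers the primary objective.

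At stake is the migraine/inter-ictal ratio. SAP 9.3.2 aims to determine whether altered gastric motility during an attack changes exposure. A patient with a markedly low attack-period value may be showing that effect, and the rule allows the value to be removed without the untrimmed ratio beside it.

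**Working it through.** **Inputs from the documents.** n = 12 and CV 40% (SAP 7); inter-subject CV up to 61% for Cmax (Protocol 3.2); 90% CI from a model with period fixed and patient random (SAP 9.3.2).

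**The plan's own figure.** Log SD = sqrt(ln(1 + 0.40²)) = 0.385. Then exp(1.645 × 0.385/√12) − 1 = 20.1%, as stated. This treats 0.385 as the SD of the within-patient log ratio, which implies a within-patient SD of 0.385/√2 = 0.27. For CV 61%, sqrt(ln(1 + 0.61²)) = 0.562.

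**Assumptions.** Log-normal data; total log SD 0.385 or 0.562; within-patient SD 0.15 to 0.27; test run on each period's log values, with repeats; patients with a deleted value dropped from the paired comparison.

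**How often the limit is crossed.** The tested value is the most extreme and is left out of the SD, so 3 SD is not a rare-event limit. The rate on clean data is n × 2 × P(t with n − 2 df > 3/√(n/(n − 1))):

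- n = 6: 31%
- n = 12: 20% (0.199)
- n = 20: 18%

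If every data set were tested at n = 12, the expected number with a crossing on clean data is 6 × 0.199 = 1.2 for the parent (3 parameters × 2 periods) and 36 × 0.199 = 7.2 over all six analytes.

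**No effect or a uniform effect (simulation, n = 12).** A crossing in either period occurs in 29 to 36% of trials per parameter. Keeping or excluding then changes the ratio by a median of 1.7 to 4.3%. Coverage of the 90% CI is 90% with all values kept and about 88 to 90% if every crossing is acted on.

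**A few patients with a large true loss (simulation, n = 12).** Each patient is affected with probability 1/12. The true ratio is exp(ln(0.2)/12) = 0.874 for an 80% loss and exp(ln(0.4)/12) = 0.926 for a 60% loss. With every crossing acted on:

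| Loss | Total log SD | True ratio | Ratio after exclusion | Coverage, excluded | Coverage, all kept |
|---|---|---|---|---|---|
| 80% | 0.385 | 0.874 | 0.93–0.94 | 52–75% | 77–87% |
| 80% | 0.562 | 0.874 | 0.90–0.91 | 63–81% | 76–88% |

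For a 60% loss, 0.926 becomes about 0.93 to 0.94 and coverage falls by about 1 to 6 points.

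**Sensitivity to the data tested.** If the test is run once on the 12 within-patient log ratios instead, clean-data coverage falls from 89.8% to 85.7%. The choice of data therefore matters and should be stated.

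**The case against.** The strongest reply is that there is no real contradiction. The general paragraph speaks of the procedure as a whole, and step 2(e) is part of it. This stands: 2(e) is loosely worded, not a rival rule of equal rank. A reader might infer from 2(e) alone that deletion is mandatory, or that the 20% crossing rate is a deletion rate. The documents support neither.

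Second, the damage depends on assumptions. No passage gives an expected loss. The only altered-absorption data, the high-fat meal result in Protocol 3.2, show a later tmax with Cmax and AUC about 20% higher. Vomiting has its own provision in SAP 8. Deleting a genuine attack-related loss would hardly be scientifically appropriate when that loss is what the study measures. These points stand, and they limit the size of the concern. They do not supply the missing comparison.

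Third, transparency exists: excluded values are documented, and a reader with the listings could recompute the untrimmed ratio. That is true, but it is not the same as reporting that ratio with its CI.

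Fourth, complete profiles are protected. In a check at within-patient SD 0.20 with one of 12 patients affected, an 80% loss in Cmax and both AUCs made all three cross in 73 to 79% of trials at total SD 0.385 and 30 to 40% at 0.562; the protection could then apply. If only Cmax is lowered, all three cross in about 1%, so it would rarely help.

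**Conclusion.** The point holds as one of pre-specification and reporting. Exclusion at n ≥ 6 is discretionary, is approved after results are known, and carries no duty to show the result with the value kept. With no effect or a uniform one the cost is small. It becomes material only if a few patients have a large true loss and the crossings are acted on. At an assumed 80% loss the ratio moves from 0.874 to about 0.93–0.94 (total log SD 0.385) or 0.90–0.91 (0.562); at 60% the shift is slight.

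A more alarming figure is tempting. If exactly one of 12 patients has an 80% loss in every trial, the ratio after exclusion at 0.385 is about 0.98 and coverage is 47 to 73%, while the all-values interval over-covers (up to nearly 100%). Much of that contrast comes from fixing the number affected. When it varies by chance, the all-values interval under-covers too, and the gap is smaller. The documents give no basis for the fixed case, so it should not be read as the plan's expected performance.

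This is a cheap improvement to the SAP.

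**What to change.** In SAP 9.3.1:

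1. In step 2(e) and the sentence on repeating the test, replace exclusion with flagging, so that both agree with the opening paragraph.
2. State that the analysis of all evaluable values is primary.
3. Extend the n < 6 reporting rule to every n, so that results with and without any flagged value are both reported.
4. State that the range test is run on the per-period log values of each analysed parameter, so that flagging does not depend on a judgement that a value looks atypical.

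Leave the vomiting provision in SAP 8 as it is.

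The cost is SAP wording and one extra result per flagged data set: on clean data about 1.2 of 6 for the parent and 7.2 of 36 over all analytes. The primary CI is wider when a true extreme is kept. With one of 12 patients affected, within-patient SD 0.20 and total SD 0.385, the mean log half-width is 0.198 instead of 0.179 for a 60% loss and 0.279 instead of 0.168 for an 80% loss. On clean data it is practically unchanged (0.143 and 0.144). Sample size is unaffected.
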